## 15.2. WHOLE BLOOD ICS

The following tables are planned for presentation (based on the Safety analysis set, in the Safety and Immunogenicity Cohort). Aeras will be responsible for performing this analysis.

- Percent antigen-specific T cell negative control-subtracted cytokine response and change from Baseline.
- Number (percentage) of responders.
- Comparisons of median negative control-subtracted cytokine response.

These tables will be provided for the following cytokine combinations (including repeat tables for the negative control for each cytokine combination):

- CD4 cells producing Positive (G,2,T,17,22) cytokine combination.
- CD4 cells producing Positive (G,2,T) cytokine combination.
- CD8 cells producing Positive (G,2,T,17,22) cytokine combination.
- CD8 cells producing Positive (G,2,T) cytokine combination.
- CD4 cells producing Positive (17) cytokine combination.
- CD4 cells producing Positive (22) cytokine combination.

The following listings are planned for presentation (based on the Safety analysis set):

- Percent antigen-specific T cell negative control-subtracted cytokine response and change from Baseline:
  - o Only derived cytokine combinations will be included in this listing.
- Percent antigen-specific T cell negative control-subtracted cytokine response and total (Ag85B and TB10.4) vaccine response:
  - o Only derived cytokine combinations will be included in this listing.
- ICS responder status based on each derived cytokine response:
  - o The responder status for each antigen will be displayed, including the overall status.

---

Document: Aeras\_C-040-404\_SAP\_V2\_0

Author: [name]

Version Number:

2.0

Version Date:

29SEP2017

Template No: CS\_TP\_BS016 – Revision 3

Reference: CS\_WI\_BS005

Effective Date: 01May2012

Copyright © 2012 Quintiles Transnational Corp. All rights reserved.

The contents of this document are confidential and proprietary to Quintiles Transnational Corp. Unauthorized use, disclosure or reproduction is strictly prohibited.

The following whole blood ICS variables, as presented in the planned TLF shells, will be contained in the data:

- Stimulation antigen:
  - o Ag85B.
  - o BCG.
  - o TB10.4.
  - o Negative control:
    - UNS.
- T cell:
  - o CD4+.
  - o CD8+.
- Cell counts and percentages (including a total cell count) of the following cytokines per stimulation antigen, study day and participant:
  - o IFN- $\gamma$  and/or TNF and/or IL-2.
  - o IFN- $\gamma$  and/or TNF and/or IL-2 and/or IL-17 and/or IL-22.
  - o IL-17.
  - o IL-22.

### 15.2.1. DERIVATIONS

#### 15.2.1.1. Positive (G,2,T,17,22)

The 'Positive (G,2,T,17,22)' (%) result per participant, T cell type, stimulation antigen and visit is derived as:

$\sum$  Cell percentages (%) where IFN – g and/or IL – 2 and / or TNF and / or IL-17 and / or IL-22 are positive.

#### 15.2.1.2. Positive (G,2,T)

The 'Positive (G,2,T)' (%) result per participant, T cell type, stimulation antigen and visit is derived as:

$\sum$  Cell percentages (%) where IFN – g and/or IL – 2 and / or TNF are positive.

#### 15.2.1.3. Positive (17)

The 'Positive (17)' (%) result per participant, stimulation antigen and visit for CD4 T cells is derived as:

$\sum$  Cell percentages (%) where IL – 17 is positive.

#### 15.2.1.4. Positive (22)

The 'Positive (22)' (%) result per participant, stimulation antigen and visit for CD4 cells is derived as:

$\sum$  Cell percentages (%) where IL – 22 is positive.

---

Document: Aeras\_C-040-404\_SAP\_V2\_0

Author: [name]

Version Number:

2.0

Version Date:

29SEP2017

Template No: CS\_TP\_BS016 – Revision 3

Reference: CS\_WI\_BS005

Effective Date: 01May2012

Copyright © 2012 Quintiles Transnational Corp. All rights reserved.

The contents of this document are confidential and proprietary to Quintiles Transnational Corp. Unauthorized use, disclosure or reproduction is strictly prohibited.

### 15.2.2. RESPONDER STATUS

The same method as for the PBMC ICS analysis will be used (refer to Section 15.1.2: Responder Status). Substitute 'Positive (G,2)' with each applicable derived cytokine combination.

## 16. SAFETY OUTCOMES

Summary and presentation of safety data will be based on the Safety analysis set, unless otherwise noted.

### 16.1. ADVERSE EVENTS (AEs)

Adverse events (AEs) will be coded using Medical Dictionary for Regulatory Activities (MedDRA) Version 16.1.

The following AE variables, as presented in the planned TLF shells, will be collected on the Adverse Event (AE) eCRF:

- Verbatim term (eCRF).
- Date started.
- Date stopped.
- Serious:
  - o Yes.
  - o No.
- Severity (refer to Section 16.1.2.1: Severity).
- Relationship to study vaccination (refer to Section 16.1.2.2: Relationship to Study Vaccination).
- Outcome:
  - o Resolved.
  - o Resolved with sequelae.
  - o Ongoing.
  - o Death.
- Did the AE cause the participant to discontinue from the study:
  - o Yes.
  - o No.
- Was treatment given:
  - o Yes.
  - o No.
- Is the AE of special interest:
  - o Yes.
  - o No.
- System Organ Class (SOC).
- Preferred Term (PT).

---

Document: Aeras\_C-040-404\_SAP\_V2\_0  
Author: [name]

Version Number: 2.0  
Version Date: 29SEP2017

Template No: CS\_TP\_BS016 – Revision 3  
Effective Date: 01May2012

Reference: CS\_WI\_BS005

The following AE variables, as presented in the planned TLF shells, will be collected on the SAE Report eCRF:

- Seriousness criterion:
  - o Death.
  - o Life-threatening.
  - o Hospitalization.
  - o Congenital anomaly/birth defect.
  - o Involved persistent disability/incapacity.
  - o Other important medical condition.
  - o Prolonged hospitalization.

### 16.1.1. DERIVATIONS

Based on the aforementioned, the following variable, as presented in the planned TLF shells, will be derived:

- Study day of the most recent vaccination:
  - o Calculated relative to Day 0 vaccination (refer to Section 6.1: Reference Start Date and Study Day).
- Relative days (start and stop):
  - o Calculated relative to most recent vaccination (refer to Section 6.1: Reference Start Date and Study Day).
- Dose at onset (most recent vaccination):
  - o Refer to Section 16.1.8: Adverse Event (AE) Dose at Onset (Most Recent Vaccination).
- Time of onset:
  - o Derived based on the relative days (start) as either of the following categories:
    - Day 0 to Day 3.
    - Day 4 to Day 7.
    - Day 8 to Day 14.
    - >= Day 15.
  - o For the overview of unsolicited AEs by severity, time of onset and relationship table, AEs with missing time to onset will be considered.

### 16.1.2. ALL ADVERSE EVENTS (AEs)

The following tables are planned for presentation:

- Overview of AEs:
  - o Number and percentage (%) of participants in each of the following categories (participants with multiple events in each category are counted only once in each category):
    - Any AE.
    - Any solicited AE.
    - Local solicited AE.
    - Systemic solicited AE.
    - SAE.
    - SAE with outcome of death.
    - Related AE.

---

Document: Aeras\_C-040-404\_SAP\_V2\_0

Author: [name]

Version Number:

2.0

Version Date:

29SEP2017

Template No: CS\_TP\_BS016 – Revision 3

Reference: CS\_WI\_BS005

Effective Date: 01May2012

Copyright © 2012 Quintiles Transnational Corp. All rights reserved.

The contents of this document are confidential and proprietary to Quintiles Transnational Corp. Unauthorized use, disclosure or reproduction is strictly prohibited.

- Severe AE.
- Related, severe AE.
- AE leading to premature study discontinuation.
- Adverse events of special interest (AESI).
- Percentage (%) of participants will be calculated relative to the total number of participants in the Safety analysis set per treatment group and cohort.
- 95% CIs:
  - Calculated for single proportion using mid-p binomial option (Clopper-Pearson method with mid-p correction).
- Number of events in each of the aforementioned categories (participants with multiple events in each category are counted multiple times in each category).
- This output will be repeated for the Safety and Immunogenicity Cohort as well as the Correlates Cohort.

All AE incidence tables will be sorted by:

- SOC (descending frequency of total number of participants with events reported).
- PT (descending frequency of total number of participants with events reported within each SOC).

All AE incidence tables presented by PT only will be sorted by:

- PT (descending frequency of total number of participants with events reported).

The following incidence table will be presented by SOC and PT:

- Incidence of AEs:
  - Number and percentage (%) of all participants with AEs summarized by SOC and PT.
  - Includes all AEs within the post-vaccination reporting windows (refer to Section 16.1.9: Adverse Event (AE) Post-vaccination Reporting Window for details on the derivation of post-vaccination reporting window).
  - This table will be repeated for the Safety and Immunogenicity Cohort.
- Incidence of AEs by dose (refer to 16.1.8: Adverse Event (AE) Dose at Onset (Most Recent Vaccination)).

The following incidence table is planned for presentation by PT only:

- Incidence of AEs:

The following listings are planned for presentation:

- Solicited and unsolicited non-serious AEs.
- AE comments.

#### 16.1.2.1. Severity

Severity will be reported on the Adverse Events eCRF as mild, moderate or severe (increasing severity).

Missing severities will not be regarded as 'worst case' severity. If any missing severity is present in the data transfer, the severity will remain missing and will be counted under the missing category in the by-severity tables. Participants with multiple events in each SOC/solicited AE category and PT are counted only once in each SOC/solicited AE category and PT at highest severity.

---

Document: Aeras\_C-040-404\_SAP\_V2\_0

Author: [name]

Version Number:

2.0

Version Date:

29SEP2017

Template No: CS\_TP\_BS016 – Revision 3

Reference: CS\_WI\_BS005

Effective Date: 01May2012

Copyright © 2012 Quintiles Transnational Corp. All rights reserved.

The contents of this document are confidential and proprietary to Quintiles Transnational Corp. Unauthorized use, disclosure or reproduction is strictly prohibited.

For the overview of unsolicited AEs by severity, time of onset and relationship table, AEs with missing severity will be considered. The participant will be counted in the missing category if the all severities are reported as missing for the relevant participant.

The following incidence tables are planned for presentation by SOC and PT:

- Incidence of AEs by highest severity.
- Incidence of AEs by highest severity by dose (refer to 16.1.8: Adverse Event (AE) Dose at Onset (Most Recent Vaccination)).

The following listing will be presented:

- Adverse events of toxicity grade 3/4:
  - o An AE of toxicity grade 3/4 is any AE for which the severity is indicated as severe.

#### 16.1.2.2. Relationship to Study Vaccination

Relationship to study vaccination will be reported on the Adverse Events eCRF as definite, probable, possible, unlikely or not related (decreasing relationship).

The relationship to study vaccination will be reported as either related or not related:

- Related AE if relationship to study vaccination is reported as:
  - o Definite.
  - o Probable.
  - o Possible.
- Not related AE if relationship to study vaccination is reported as:
  - o Unlikely.
  - o Not related.

Missing relationship to study vaccination will not be regarded as 'worst case' relationship to study vaccination. If any missing relationship to study vaccination is present in the data transfer, that relationship to study vaccination is to remain missing and will be counted in the missing category in the by-relationship tables. Participants with multiple events in each SOC/solicited AE category and PT are counted only once in each SOC/solicited AE category and PT at the strongest relationship.

For the overview of unsolicited AEs by severity, time of onset and relationship table, AEs with missing relationship to study vaccine will be considered. The participant will be counted in the missing category if the all relationship to study vaccine is reported as missing for the relevant participant.

The following incidence tables are planned for presentation by SOC and PT:

- Incidence of related AEs.
- Incidence of related AEs by dose (refer to 16.1.8: Adverse Event (AE) Dose at Onset (Most Recent Vaccination)).
- Incidence of related AEs by highest severity.
- Incidence of related AEs by highest severity and dose (refer to 16.1.8: Adverse Event (AE) Dose at Onset (Most Recent Vaccination)).

---

Document: Aeras\_C-040-404\_SAP\_V2\_0  
Author: [name]

Version Number: 2.0  
Version Date: 29SEP2017

Template No: CS\_TP\_BS016 – Revision 3  
Effective Date: 01May2012

Reference: CS\_WI\_BS005

The following incidence tables are planned for presentation by PT only:

- Incidence of related AEs.

### 16.1.3. UNSOLICITED ADVERSE EVENTS (AEs)

The following overview table is planned for presentation:

- Overview of unsolicited AEs by severity, time of onset and relationship:
  - o Number and percentage (%) of participants in each of the following categories (participants with multiple events in each category are counted only once in each category, worst case/shortest time to onset):
    - Severity (refer to Section 16.1.2.1: Severity).
    - Time of onset (refer to Section 16.1.1: Derivations).
    - Relationship (refer to Section 16.1.2.2: Relationship to Study Vaccination).
  - o Number of events in each of the aforementioned categories (participants with multiple events in each category are counted multiple times in each category).
  - o Includes all unsolicited AEs, SAEs as well as AEs of special interest within the post-vaccination reporting window (refer to Section 16.1.9: Adverse Event (AE) Post-vaccination Reporting Window for details on the derivation of the post-vaccination reporting window).
  - o 95% CIs:
    - Calculated for single proportion using mid-p binomial option (Clopper-Pearson method with mid-p correction).
  - o This table will be repeated for the Safety and Immunogenicity Cohort as well as the Correlates Cohort.

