#### 7.5.1 Adverse Events

The safety profile of BCG revaccination, AERAS-404 and saline placebo will be described by treatment group. The primary variable for evaluation of the safety profile will be the number and percentage of unsolicited and solicited adverse events recorded at all available post-vaccination time points. For all presentations of adverse events, additional summaries based on reporting period of adverse events following each study vaccination may also be presented.

The number (percentage) of subjects with adverse events will be summarized by MedDRA system organ class (SOC) and preferred term (PT). Additional summaries will present the number (percentage) of subjects with adverse events by severity and by relationship to study vaccine; each subject will be counted once per preferred term at the greatest severity or most related state recorded for that term.

Separate summaries of the number (percentage) of subjects with solicited adverse events will also be presented. Solicited adverse events will also be summarized by severity and relationship to study vaccine; each subject will be counted once per preferred term at the greatest severity or most related state recorded for that term.

Listings will be provided for subjects with serious adverse events and adverse events of special interest.

Listings will be provided for subjects who have discontinued prematurely due to an adverse event.

The number (percentage) of subjects with post-vaccination clinical laboratory values or vital sign values recorded as newly abnormal following study vaccination and meeting toxicity mild criteria (Grade 1) or above as specified in the Toxicity Table (Appendix C) will be tabulated at each post-vaccination time point and overall. Clinical laboratory and vital sign abnormalities will also be reported as adverse events and will be included in the summary of adverse events.

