### 3. STUDY DESIGN

#### 3.1. GENERAL DESCRIPTION

A Phase II, randomized, 3-arm, placebo-controlled, partially blinded clinical trial that was conducted in 990 healthy HIV-uninfected, QFT-GIT negative, previously BCG vaccinated adolescents. Participants were recruited from high schools or directly from the community.

Participants were enrolled in two sequential cohorts:

- Safety and Immunogenicity Cohort:
  - o First 90 participants (30 from each arm).
  - o More intensive collection of safety data.
  - o Selected immunogenicity assays (including whole blood intracellular cytokine staining [ICS]).
  - o Data reviewed by the data monitoring committee (DMC), principal investigator and local medical monitor.
- Correlates Cohort:
  - o Remaining 900 participants.

All 990 participants in the study were evaluated for:

- Safety outcomes.
- Biomarker outcomes.
- Prevention of *Mtb* infection.

Within each cohort, participants were randomized in a 1:1:1 ratio to one of the following treatment groups:

- H4:IC31:
  - o 15 mcg H4/500 nmol IC31.
  - o Two doses (administered on Day 0 and Day 56).
  - o Intramuscular injection.
- Placebo:
  - o Saline volume equivalent to the H4:IC31 injection.
  - o Two doses (administered on Day 0 and Day 56).
  - o Intramuscular injection.

---

Document: Aeras\_C-040-404\_SAP\_V2\_0

Author: [name]

Version Number:

2.0

Version Date:

29SEP2017

Template No: CS\_TP\_BS016 – Revision 3

Reference: CS\_WI\_BS005

Effective Date: 01May2012

Copyright © 2012 Quintiles Transnational Corp. All rights reserved.

The contents of this document are confidential and proprietary to Quintiles Transnational Corp. Unauthorized use, disclosure or reproduction is strictly prohibited.

- BCG:
  - o 2-8 x 10^5 CFU.
  - o One dose (administered on Day 0).
  - o Intradermal injection.

Randomization to the H4:IC31 and Placebo treatment groups was double-blinded. Since BCG causes a recognizable local injection site reaction, the BCG revaccination treatment group was not blind. Laboratory staff performing QFT-GIT, immunogenicity and correlates assays were blinded to all three treatment groups. Planned randomization of participants is specified in Table 1: Planned Enrollment by Treatment Group and Cohort, below:

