#### **16.1.9. ADVERSE EVENT (AE) POST-VACCINATION REPORTING WINDOW**

All SAEs and AESIs will be collected through database lock.

All unsolicited AEs will be collected during the 28-day reporting window following each study vaccination. The reporting window is defined in terms of the relevant scheduled study visit coinciding with the 28-day window following the relevant dose.

Solicited systemic adverse events will be collected during the 7-day reporting window following each study vaccination (diary cards will be used for 7 days following each study vaccination for the Safety and Immunogenicity Cohort only).

Solicited and unsolicited local injection site reaction adverse events will be collected:

- BCG treatment group:
  - o 84-day reporting window following study vaccination.
- H4:IC31 and Placebo treatment groups:
  - o 28-day reporting window following each vaccination.

---

Document: Aeras\_C-040-404\_SAP\_V2\_0  
Author: [name]

Version Number: 2.0  
Version Date: 29SEP2017

Template No: CS\_TP\_BS016 – Revision 3  
Effective Date: 01May2012

Reference: CS\_WI\_BS005

Refer to Table 4: General Adverse Event (AE) Post-vaccination Reporting Windows below for the relevant post-vaccination reporting windows as defined in terms of scheduled study visits:

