**Table 4: General Adverse Event (AE) Post-vaccination Reporting Windows**

Adverse Event Type	Treatment Group	Dose at Onset	Post-vaccination Reporting Window	
			Scheduled Study Visit	Protocol Specified Visit Window
Unsolicited AE	All	Day 0	Study Day 28	28 days following Study Day 0
	H4: IC31 Placebo	Day 56	Study Day 84	28 days following Study Day 56
Local Solicited AEs	BCG	Day 0	Study Day 84	84 days following Study Day 0
	H4: IC31 Placebo	Day 0	Study Day 28	28 days following Study Day 0
	H4: IC31 Placebo	Day 56	Study Day 84	28 days following Study Day 56
Systemic Solicited AEs	All	Day 0	Study Day 7	7 days following Study Day 0
	H4: IC31 Placebo	Day 56	Study Day 63	7 days following Study Day 56
SAEs and AEs of special interest	All	All	-	Through database lock

If the relevant scheduled study visit occurred within the protocol specified visit window, all AEs with start date through the relevant scheduled study visit will be included in the reporting period. If the relevant scheduled study visit occurred outside the protocol specified visit window, only include AEs with start date through either 7, 28 or 84 days will be included.

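### The unsolicited-AE overview and the systemic-solicited row of the all-AE overview set one BCG collection window beside two for placebo and H4:IC31, with no split by dose

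*SAP*

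**What the plan says.** Under SAP 3.1, BCG is given on Day 0 only; placebo and H4:IC31 (AERAS-404 in the protocol) are given on Days 0 and 56. SAP 16.1.9 and its Table 4 set the AE windows:

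- **Unsolicited:** "All unsolicited AEs will be collected during the 28-day reporting window following each study vaccination". Table 4 gives every arm "28 days following Study Day 0", and gives H4:IC31 and placebo alone a second window, "28 days following Study Day 56".
- **Systemic solicited:** 7 days after each dose.
- **Local injection-site:** 84 days on BCG; 28 days after each dose on the other arms.
- **SAEs and AESIs:** through database lock in every arm.

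Protocol 7.5.1 makes the primary safety variable the "number and percentage of unsolicited and solicited adverse events recorded at all available post-vaccination time points", and leaves summaries by vaccination optional.

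Two overview tables follow. The unsolicited one (SAP 16.1.3), titled "Overview of unsolicited AEs by severity, time of onset and relationship", reports participants and events in each of those categories. Its onset categories run from the most recent dose (SAP 16.1.1), so they pool doses too. The all-AE overview (SAP 16.1.2) has rows for any AE, local and systemic solicited, related, severe, SAE, AESI and others, and states: "Percentage (%) of participants will be calculated relative to the total number of participants in the Safety analysis set per treatment group and cohort". Both carry 95% mid-p intervals; the SAP lists none for any other AE table.

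By-dose tables are planned for all AEs, highest severity and related AEs (SAP 16.1.2 to 16.1.2.2) and for solicited AEs (SAP 16.1.4).

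**The concern.** The safety profile of BCG revaccination is a primary objective, and placebo is the only control arm. In the unsolicited overview and in the systemic-solicited row, the percentage on BCG reflects half the collection time of the percentage printed beside it. Two arms with the same background rate are then expected to look different, with BCG appearing the safer. A real BCG excess in unsolicited or systemic events could be masked.

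Intensity of collection differs as well. Protocol Table 3-1 schedules unsolicited-AE collection on BCG at Days 0, 7 and 28, three contacts. Table 3-2 schedules it on the other arms at Days 0, 3, 7, 28, 56, 63, 70 and 84, eight contacts.

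**Working it through.** The documents state no unsolicited-AE rate and no between-arm ratio, so there is no plan figure to reproduce. The inputs are the windows in SAP Table 4 and 330 participants per arm (SAP Table 1).

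**1. Window ratios, BCG to placebo.** Unsolicited 28/(28+28) = 0.50; with the +5-day visit window, 33/66 = 0.50. Systemic solicited 7/14 = 0.50. Local 84/56 = 1.5. SAEs and AESIs follow one rule in all arms.

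**2. Event counts.** With the same daily background rate, the expected ratio equals the window ratio, 0.50. If only a fraction u of participants receive the second dose it is 1/(1+u): 0.53 at u = 90%, 0.56 at 80%.

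**3. Percentage of participants with at least one unsolicited AE.** Let p be the risk in one 28-day window (assumed). With independent windows and full second-dose uptake, the two-window risk is 1-(1-p)^2, and the ratio is p/[1-(1-p)^2] = 1/(2-p).

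| Assumed p | BCG | Placebo | Ratio |
|---|---|---|---|
| 5% | 5.0% | 9.75% | 0.51 |
| 10% | 10% | 19% | 0.53 |
| 30% | 30% | 51% | 0.59 |
| 50% | 50% | 75% | 0.67 |

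**4. Relaxing the assumptions.** Some participants report more than others. With gamma frailty of shape k and mean m events per window, set (1+m/k)^(-k) = 1-p; the two-window risk is then 1-(1+2m/k)^(-k). For k from 0.5 to 2 the ratio is 0.62 to 0.70 at p = 30% and 0.71 to 0.80 at p = 50%. Without frailty but with 80% second-dose uptake, the ratio at p = 30% is 0.30/(0.30 + 0.70 × 0.30 × 0.80) = 0.64.

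**5. How it would look with intervals.** These are Wald intervals, q ± 1.96 × sqrt[q(1-q)/330], as an approximation to the planned mid-p intervals.

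- p = 10%: 6.8-13.2% on BCG, 14.8-23.2% on placebo. They do not overlap.
- p = 30%: 25.1-34.9% and 45.6-56.4%. They do not overlap.
- p = 5%: 2.6-7.4% and 6.5-13.0%. They overlap slightly.

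**6. Rows of the all-AE overview.** There is no unsolicited row, so steps 2 to 5 apply to the table in SAP 16.1.3. The systemic-solicited row carries the 7 against 14 day imbalance. The any-AE, related and severe rows also include local reactions, where BCG has the longer window. The protocol treats solicited local reactions as causally related (Section 5.7), its Toxicity Table puts ulceration or drainage at Grade 3, and Section 5.4 records Grade 3 as severe.

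**7. What the by-dose tables supply.** Those in SAP 16.1.4 give systemic solicited events after dose 1 in all arms, which is an equal 7-day window. Those in SAP 16.1.2 to 16.1.2.2 allow individual non-local terms to be compared after dose 1. Their totals are not on equal windows: after dose 1, local events run to Day 84 on BCG and for 28 days on placebo. None gives an unsolicited-only total.

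**The case against.** The strongest reply is that the safety analysis is descriptive. The safety objective asks for the profile of each product, and only the efficacy objective names placebo as comparator (Protocol 2.1). No between-arm AE test is planned, and the intervals are for single proportions. Incidence per regimen as given is a legitimate summary. The by-dose tables answer much of the need, and table layout rests partly on shells outside these documents. Most of this stands. It does not remove the point, because the arms appear in the same tables with intervals, and no listed table gives an unsolicited total on equal windows.

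A reader might go further and infer that the headline AE tables make BCG look about half as reactogenic as placebo. The documents do not support that:

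- Reactogenicity is captured mainly by solicited reactions, and for local ones BCG has the longer window.
- One half fits event counts and uncommon events. For common events the participant ratio is well above one half, and p is assumed throughout.
- On the any-AE, related and severe rows BCG may well look worse. Protocol 1.4 reports redness in all subjects after BCG in study C-013-404, and Protocol 1.6 describes a superficial ulcer as part of the usual course.

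The size in the unsolicited table could also be smaller than shown. The text of SAP 16.1.9 gives unsolicited injection-site events 84 days on BCG, while Table 4 gives all unsolicited AEs 28 days after Day 0. If the text governs and such events make up a share s of the daily rate in both arms, the event-count ratio is [28(1-s)+84s]/56 = 0.5 + s, for example 0.60 at s = 10%.

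**Conclusion.** The point holds for the unsolicited-AE overview and for the systemic-solicited row of the all-AE overview. With identical background rates the expected BCG/placebo ratio in the unsolicited overview is 0.50 for event counts. For participants it is 0.51 to 0.67 for an assumed 28-day risk of 5% to 50%, and nearer 1 with frailty or incomplete second-dose uptake. These figures assume a constant background rate and the Table 4 windows.

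The net direction of the any-AE, related and severe rows cannot be determined from the documents. SAE and AESI rows are unaffected. For systemic solicited events the gap is mainly the lack of equal-window intervals, since like-for-like counts are already planned. This is a reporting weakness worth correcting; it does not invalidate the safety analysis.

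**What to change.** In both overviews, add a panel limited to AEs with onset on relative Days 0-28 after the first dose (Days 0-7 for systemic solicited events), for all three arms, with the same mid-p intervals. Use it whenever BCG is set beside placebo. The cut must be on relative day as well as dose: on BCG every later event is assigned to dose 1, so dose at onset alone does not equalise the windows.

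Keep the pooled panel for H4:IC31 versus placebo, where the windows match, for BCG local reactions after Day 28, and for SAEs and AESIs. Footnote the window lengths by arm, the extra Day 3 contact on placebo and H4:IC31, and the open-label BCG arm. Reconcile SAP 16.1.9 with Table 4 on the window for unsolicited injection-site events.

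The cost is SAP wording and one panel in each of two tables. Relative day and dose at onset are already derived (SAP 16.1.1 and 16.1.8), and no new data are needed. The final analysis follows database lock and unblinding (SAP 4.3), so the panel can be specified beforehand. The downside is that the BCG-placebo panel uses only first-dose placebo data, and that unequal contacts and open-label reporting remain.
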